7.8 Total Amount of Blood

WAS:

Table 11 Blood Volume

Sample Type	Number of Samples	Sample Volume (mL)	Total Volume (mL)
Clinical Laboratory Tests	6	7.0 (12.0)†	47.0
Pregnancy Test (Female Subjects Only)	3	3.0	9.0
FSH Test (Postmenopausal Female Subjects Only)	1	3.0	3.0
Mirabegron Pharmacokinetics	34	5.0	170.0
Total			217.0 for males 226.0 for females 220.0 for postmenopausal females

FSH: follicle-stimulating hormone

† Includes serology test at screening.

IS AMENDED TO:

Table 12 Blood Volume

Sample Type	Number of Samples	Sample Volume (mL)	Total Volume (mL)
Clinical Laboratory Tests	6	7.0 (12.0)†	47.0
Pregnancy Test (Female Subjects Only)	3	3.0	9.0
FSH Test (Postmenopausal Female Subjects Only)	1	3.0	3.0
Mirabegron Pharmacokinetics	34	5.0	170.0 136.0
Total			217.0 183.0 for males 226.0 192.0 for females 220.0 186.0 for postmenopausal females

FSH: follicle-stimulating hormone

† Includes serology test at screening.

10 Operational Considerations 10.1 Data Collection
WAS:
In the interest of collecting data in the most efficient manner, the investigator or designee should record data (including clinical laboratory values, if applicable) in the eCRF within 10 working days after the subject's visit.
IS AMENDED TO:
In the interest of collecting data in the most efficient manner, the investigator or designee should record data (including clinical laboratory values, if applicable) in the eCRF within 10 working days after the subject's visit. The data will be entered after HGRAC data filing approval if required by site.

III. Nonsubstantial amendment rationale:

Rationale for nonsubstantial designation
All revisions made to the protocol are administrative in nature and do not impact the safety or scientific value of the clinical study.

## I. LIST OF ABBREVIATIONS AND KEY TERMS

### List of Abbreviations

Abbreviations	Description of abbreviations
AE	adverse event
ANOVA	analysis of variance
AUC	area under the concentration-time curve
AUC inf	area under the concentration-time curve from the time of dosing extrapolated to time infinity
AUC inf (%extrap)	area under the concentration-time curve from the time of dosing extrapolated to time infinity as a percentage of total area under the concentration-time curve
AUC last	area under the concentration-time curve from the time of dosing to the last measurable concentration
BMI	body mass index
CI	confidence interval
CL	apparent total systemic clearance after extravascular dosing
C max	maximum concentration
CSR	clinical study report
ECG	electrocardiogram
ESV	end-of-study visit
IP	investigational product
LS	least square(s)
MedDRA	Medical Dictionary for Regulatory Activities
Mg	milligrams
PD	protocol deviation
PK	pharmacokinetic
PKAS	pharmacokinetic analysis set
SAE	serious adverse event
SAF	safety analysis set
SAP	statistical analysis plan
t ½	terminal elimination half-life
TEAE	treatment-emergent adverse event
t lag	time prior to the time corresponding to the first measurable (nonzero) concentration
t max	time of maximum concentration
V z /F	apparent volume of distribution during the terminal elimination phase after extravascular dosing

## List of Key Terms

Terms	Definition of terms
Baseline	Assessments of subjects as they enter a study before they receive any dosing.
Endpoint	Variable that pertains to the efficacy or safety evaluations of a study. Note: Not all endpoints are themselves assessments since certain endpoints might apply to populations or emerge from analysis of results. That is, endpoints might be facts about assessments (e.g., prolongation of survival).
Enroll	To register or enter a subject into a study. Note: Once a subject has received the IP or placebo, the protocol applies to the subject.
Intervention	The drug, device, therapy or process under investigation in a study that is believed to have an effect on outcomes of interest in a study (e.g., health-related quality of life, efficacy, safety and pharmacoeconomics).
Investigational period	Period of time where major interests of protocol objectives are observed, and where the test product or comparative drug (sometimes without randomization) is given to a subject, and continues until the last assessment after completing administration of the test product or comparative drug.
Randomization	The process of assigning subjects to treatment or control groups using an element of chance to determine assignments in order to reduce bias. NOTE: Unequal randomization is used to allocate subjects into groups at a differential rate; for example, 3 subjects may be assigned to a treatment group for every 1 assigned to the control group.
Screen failure	Potential subject who signed the ICF but did not meet 1 or more criteria required for participation in the study and was not randomized.
Screening	A process of active consideration of potential subjects for randomization in a study.
Screening period	Period of time before entering the investigational period, usually from the time when a subject signs the consent form until just before the test product or comparative drug (sometimes without randomization) is given to a subject.
Study period	Period of time from the first study site initiation date to the last study site completing the study.
Variable	Any quantity that varies; any attribute, phenomenon or event that can have different qualitative or quantitative values.

## 1 INTRODUCTION

This Statistical Analysis Plan (SAP) contains technical and detailed elaboration of the principal features of the analysis described in the protocol, and includes procedures for executing the statistical analysis to fulfil the objectives of the study.

The final SAP will be approved prior to database hardlock.

Changes from the planned analyses in the final SAP that impact the statistical analyses will be documented in the Clinical Study Report (CSR).

## 2 STUDY OBJECTIVE(S) AND DESIGN

### 2.1 Study Objective(s)

The primary objective of this study is to determine the effect of food on the pharmacokinetics of single oral doses of mirabegron in healthy Chinese male and female subjects.

The secondary objective is to evaluate the safety and tolerability of single oral doses of mirabegron in healthy Chinese male and female subjects.

The exploratory objective is to evaluate the pharmacokinetics of single oral doses of mirabegron in healthy Chinese male and female subjects.

### 2.2 Study Design

The study follows an open-label, randomized, 2-period, single oral dose crossover design at 2 dose levels in healthy Chinese male and female subjects. Each subject will participate in 2 periods separated by a washout of at least 10 days between IP administrations in each period.

Dose (mg)	Sequence	n	Period 1	Period 2
25	1	6	Mirabegron (low-fat)	Mirabegron (fasted)
	2	6	Mirabegron (fasted)	Mirabegron (low-fat)
50	1	6	Mirabegron (low-fat)	Mirabegron (fasted)
	2	6	Mirabegron (fasted)	Mirabegron (low-fat)

The dose under fed conditions will be administered following a low-fat breakfast (total calories approximately 450 kcal, with approximately 70 kcal from fat).

Pharmacokinetic samples will be collected predose on day 1 of each period and at multiple time points following each dose (see the Schedule of Assessments in the protocol.)

The study will be completed with an end-of-study visit (ESV). The ESV will take place 5 to 9 days after the last pharmacokinetic sample is collected or at early discontinuation from the study.

Details of the schedule of clinical assessments are available in the protocol.

## 2.3 Randomization

Randomization will be allocated through blocks. There will be no stratification variables.

## 3 SAMPLE SIZE

A total of 24 subjects (12 subjects per dose group) will be enrolled. Subjects who discontinue early from the study may be replaced at the discretion of the sponsor.

Based on data from Study 178-CL-091, a Chinese phase 1 study, the intrasubject coefficient of variation (CV) for pharmacokinetic parameters  $AUC_{inf}$ ,  $AUC_{last}$  and  $C_{max}$  of the 50 mg mirabegron dose are estimated to be between 33% and 60%. Assuming the underlying variability is similar to 60% and an observed ratio between fasted and fed conditions of 100%, the 90% CI will lie within (60, 167) with > 80% probability.

## 4 ANALYSIS SETS

In accordance with International Conference on Harmonization (ICH) recommendations in guidelines E3 and E9, the following analysis sets will be used for the analyses.

The determination of whether subjects are included or excluded from the safety analysis set will be made prior to database hard-lock.

### 4.1 Safety Analysis Set

The safety analysis set (SAF) consists of all subjects who receive at least 1 dose of IP. The SAF will be used for all summaries and analyses of the safety data.

### 4.2 Pharmacokinetics Analysis Set

The pharmacokinetic analysis set (PKAS) consists of all subjects who receive at least 1 dose of IP for which concentration data are available to facilitate derivation of at least 1 primary pharmacokinetic parameter. Inclusion of subjects in the PKAS with missing data or major protocol deviations will be considered by the pharmacokineticist on a case-by-case basis.

The PKAS will be used for all summaries and analyses of the pharmacokinetic data.

## 5 PHARMACOKINETIC AND SAFETY ENDPOINTS

### 5.1 Pharmacokinetic Endpoint (Primary)

The primary PK endpoints will be Mirabegron plasma PK parameters:  $AUC_{inf}$ ,  $AUC_{last}$  and  $C_{max}$ .

### 5.2 Safety Endpoints (Secondary)

Safety will be assessed by evaluation of the following endpoints:

- Nature, frequency and severity of AEs
- Clinical laboratory tests (biochemistry, hematology and urinalysis)

- Vital signs (blood pressure, body temperature and pulse)
- Routine 12-lead ECG

### **5.3 Exploratory Endpoints**

The exploratory PK endpoints will be Mirabegron plasma PK parameters  $AUC_{inf}(\%extrap)$ ,  $CL/F$ ,  $t_{1/2}$ ,  $t_{max}$ ,  $t_{lag}$  and  $V_z/F$ .

## **6 STATISTICAL METHODOLOGY**

### **6.1 General Considerations**

In general, all data will be summarized with descriptive statistics (n, mean, SD, median, minimum and maximum) for continuous endpoints, and frequency and percentage for categorical endpoints, unless otherwise specified. Percentages by categories will be based on the number of subjects with no missing data (i.e., will add up to 100%).

For each sequence, the number and percentage of subjects will be characterized for all randomized subjects and by each analysis set.

### **6.2 Study Population**

#### **6.2.1 Disposition of Subjects**

The number and percentage of subjects who completed and discontinued dosing and reasons for dosing discontinuation will be presented for all randomized subjects and for subjects in the SAF by dose group, sequence and overall. Similar tables for investigational period disposition and follow-up disposition will also be presented for all randomized subjects by dose group, sequence and overall. All disposition details and dates of first and last evaluations for each subject will be listed.

#### **6.2.2 Protocol Deviations**

The major protocol deviations are defined as follows:

- PD1 - Entered into the study even though they did not satisfy entry criteria,
- PD2 - Developed withdrawal criteria during the study and was not withdrawn,
- PD3 - Received incorrect dose,
- PD4 - Received excluded concomitant treatment.

Major protocol deviations will be listed.

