7.3.7 Special Situations

Certain special situations observed in association with the IP, such as incorrect administration (e.g., wrong dose of IP or background therapy) are collected in the eCRF, as protocol deviations per [Section [10.3](#) Major Protocol Deviations] or may require special reporting, as described below. These special situations are not considered AEs, but are required to be communicated to Astellas as per the timelines defined below.

If a special situation is associated with, or results in, an AE, the AE is to be assessed separately from the special situation and captured as an AE in the eCRF. If the AE meets the definition of an SAE, the SAE is to be reported as described in [Section [12.4.5](#) Reporting Procedures for Serious Adverse Events] and the details of the associated special situation are to be included in the clinical description on the special situation worksheet.

The special situations are:

- Pregnancy
- Medication error, overdose and “off-label” use
- Misuse/abuse

- Occupational exposure
- Suspected drug-drug interaction

Instructions and procedures for reporting special situations are provided in [Appendix 12.4.6 Reporting Procedures for Special Situations].

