9.9 Major Protocol Deviations

Major protocol deviations as defined in [Section [10.3](#) Major Protocol Deviations] will be listed.

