10.3 Major Protocol Deviations

A protocol deviation is generally an unplanned excursion from the protocol that is not implemented or intended as a systematic change. All deviations from the protocol are to be recorded. A protocol waiver is a documented prospective approval of a request from an investigator to deviate from the protocol. Protocol waivers are strictly prohibited.

The investigator is responsible for ensuring the study is conducted in accordance with the procedures and evaluations described in this protocol and must protect the rights, safety and well-being of subjects. The investigator should not implement any deviation from, or changes of, the protocol, unless it is necessary to eliminate an immediate hazard to subjects.

A major protocol deviation is one that may potentially impact the completeness, accuracy or reliability of data contributing to the primary endpoint or affect the rights, safety or well-being of a subject. Major protocol deviations will have additional reporting requirements.

When a major deviation from the protocol is identified for an individual subject, the investigator or designee must ensure the sponsor is notified. The sponsor will follow up with the investigator, as applicable, to assess the deviation and the possible impact to the safety and/or pharmacokinetic parameters of the subject to determine subject continuation in the study.

The major protocol deviation criteria that will be summarized at the end of the study are as follows:

PD1 - Entered into the study even though the subject did not satisfy entry criteria

PD2 - Developed withdrawal criteria during the study and was not withdrawn

PD3 - Received incorrect dose

PD4 - Received excluded concomitant treatment

The investigator will also assure that deviations meeting IRB/IEC and appropriate regulatory authorities' criteria are documented and communicated appropriately. All documentation and communications to the IRB/IEC and appropriate regulatory authorities will be provided to the sponsor and maintained within the trial master file.

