12.2.4 Quality Assurance

The sponsor is implementing and maintaining quality assurance (QA) and quality control (QC) systems with written SOPs to ensure that studies are conducted and data are generated, documented, recorded, and reported in compliance with the protocol, GCP and applicable regulatory requirement(s). Where applicable, the QA and QC systems and written SOPs of the CRO will be applied.

The sponsor or sponsor's designee may arrange to audit the study at any or all study sites and facilities. The audit may include on-site review of regulatory documents, CRFs and source documents. Direct access to these documents will be required by the auditors.

To support quality around subject safety and reliability of study results, quality tolerance limits (QTLs) are defined and monitored. QTLs represent the acceptable variation of study data, taking into consideration the current state of medical and statistical knowledge about the variables to be analyzed as well as the statistical design of the study. It is a level, point, or value associated with a parameter that should trigger an evaluation if a deviation is detected

to determine if there is a possible systematic issue (i.e., a trend has occurred). The QTLs defined for this study are provided below.

Table 7 Quality Tolerance Limit

QTL #: Name and Parameter	Definition	Parameter Justification
QTL1: Pharmacokinetic sample collection compliance	% of pharmacokinetics samples that are not collected or collected outside the allowed collection window	A high percentage of pharmacokinetic samples missed or collected outside of the collection window can have an impact on the assessment of the pharmacokinetic parameters
QTL2: Time of meal intake and IP administration compliance	% of meal intake and IP administration that are conducted outside the allowed time window	A high percentage of food intake and IP administration conducted outside of the designated time window can have an impact on the evaluation of the food effect

IP: investigational product; QTL: quality tolerance limit

Additional information regarding the QTL and limit justification, as well as associated activities can be found in STL-3458 QTL monitoring plan.

QTL Management Activities:

- For control of risks associated with QTL1: Pharmacokinetic sample collection compliance, refer to the Schedule of Assessments [Table 1] and [Section 7.2.6 Order of Assessments]

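### Does SAP 6.2.2 narrow the protocol's meaning of a major protocol deviation in a way that needs correcting?

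*SAP*

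**What the plan says.** SAP 6.2.2 opens with "The major protocol deviations are defined as follows" and gives four categories: entry criteria not met (PD1), withdrawal criteria met without withdrawal (PD2), wrong dose (PD3) and excluded concomitant treatment (PD4). It then states "Major protocol deviations will be listed".

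Protocol 10.3 has a test rather than a list: "A major protocol deviation is one that may potentially impact the completeness, accuracy or reliability of data contributing to the primary endpoint", or one that affects a subject's rights, safety or well-being. Later in that section the same four categories follow the sentence "The major protocol deviation criteria that will be summarized at the end of the study are as follows". Protocol 9.9, in the statistical part, says that "Major protocol deviations as defined in" section 10.3 will be listed.

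The term is used in one analysis decision. Under protocol 9.2.2 and SAP 4.2, the pharmacokineticist considers case by case whether subjects with missing data or major deviations belong in the pharmacokinetic analysis set (PKAS).

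**The concern.** One term has two meanings. A programmer who follows SAP 6.2.2 literally lists only PD1 to PD4. One who follows protocol 9.9 lists everything that meets the 10.3 test. The SAP also plans no summary, although 10.3 speaks of one.

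The difference seems to fall where it matters most. The study estimates a food effect, and the quality tolerance limits in protocol 12.2.4 single out two kinds of non-compliance. Of mistimed or missed samples it says that a high percentage "can have an impact on the assessment of the pharmacokinetic parameters"; of meal and dosing times, that a high percentage "can have an impact on the evaluation of the food effect". Neither is named in PD1 to PD4. If such an event went unlisted and so escaped the PKAS review, a subject in the wrong food state could be analysed under the assigned label and pull the fed/fasted ratio towards 100%.

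**Working it through.** The plan gives no figure to reproduce on this point. The check is to follow each kind of event through the two documents.

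| Event | Protocol | SAP | Difference |
|---|---|---|---|
| Falls under PD1 to PD4 | Recorded, listed (10.3, 9.9) | Listed (6.2.2) | None in the listing |
| Missed sample | Recorded (10.3); reaches PKAS review as missing data (9.2.2) | Reaches PKAS review as missing data (4.2) | Listing only |
| Wrong food state | Recorded (10.3); listed if it meets the 10.3 test (9.9); PKAS review (9.2.2) | Listed if read as PD3; otherwise possibly not | Listing only |
| Affects rights, safety or well-being only | Recorded, listed (10.3, 9.9) | Possibly not listed | Listing only |

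**Capture.** Protocol 10.3 requires all deviations to be recorded and the sponsor to be notified of major ones, with the possible effect on the subject's pharmacokinetic parameters assessed. Protocol 7.3.7 adds that special situations such as incorrect administration "are collected in the eCRF, as protocol deviations per" section 10.3. Dosing is supervised and its time documented (6.4). None of this depends on SAP 6.2.2.

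**Analysis.** Data enter or leave the ANOVA of SAP 6.5.3 through the PKAS decision. SAP 4.2 repeats the protocol's rule and does not confine the review to subjects in the 6.2.2 listing.

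**Listed or summarized.** SAP 6.2.2 matches protocol 9.9, which also plans a listing. The tension is between 9.9 and 10.3 inside the protocol. The SAP did not create it.

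**Scale of a mishandled event.** Protocol 2.1.1 reports low-fat reductions of about 64% to 75% in Cmax and 47% to 51% in AUCinf, so fed/fasted ratios r of 0.25 to 0.36 and 0.49 to 0.53. Assume that one of the 12 subjects in a dose group ate nothing and was analysed as fed. That subject's expected log ratio is 0, and each subject has weight 1/12 in the balanced design, so:

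observed ratio = exp(ln(r) × 11/12)

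- Cmax: 0.25 becomes 0.281; 0.36 becomes 0.392
- AUCinf: 0.49 becomes 0.520; 0.53 becomes 0.559

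The shift is a factor of r^(−1/12), from 1.054 (r = 0.53) to 1.122 (r = 0.25). For comparison, the 90% CI extends from the estimate by a factor of exp(t × σ × √(0.5 × (1/6 + 1/6))), with t(0.95, 10) = 1.812 and σ = √ln(1 + CV²). For the planning CVs of 33% and 60% (protocol 9.1), σ is 0.3215 and 0.5545, and the factors are 1.27 and 1.51. The shift is smaller than the half-width in every case, and protocol 9.6.3 sets no acceptance limit for it to cross. It comes from including the period under the wrong label and is the same whether or not the event appears in a listing.

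**The case for a change.** The best argument for acting is that the contradiction is certain and would take only a few SAP sentences to remove. The SAP calls itself an elaboration of the protocol's analysis and gives no reason for narrowing the term. In an open-label study with 12 subjects per dose group, the term that triggers PKAS review should have one meaning. Reading PD3 as covering food state is also a stretch, because it speaks of dose.

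The mismatch in wording stands, and a deviation in food condition might be left out of a listing built strictly from SAP 6.2.2. The rest is weaker:

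- Protocol 10.3 itself calls PD1 to PD4 the major deviation criteria, so the SAP's wording is a loose paraphrase of the protocol and not a new rule.
- The tolerance limits in 12.2.4 are study-wide percentages that prompt a search for a systematic problem. They are not subject-level classes of deviation, so their absence from PD1 to PD4 is no defect.
- A fixed rule for leaving out an affected period would replace the planned case-by-case review with a preference. It does not follow from a mismatch in a definition.
- SAP 4 dates the inclusion decision before hard-lock for the safety set only. That is missing detail on a separate matter and does not depend on how a major deviation is defined.

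**Conclusion.** No change follows. SAP 6.2.2 turns the protocol's reporting categories into a definition, which is a clerical slip. Its reach is the content of one listing. The effect of that wording on the ANOVA, the fed/fasted ratios and their 90% CIs is zero, because inclusion is governed by SAP 4.2 and protocol 9.2.2, which agree.

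This rests on deviations being recorded as protocol 10.3 requires, and on the pharmacokineticist reviewing all recorded deviations and not only those in the 6.2.2 listing, which the text allows. An analyst with both documents would take the definition from 10.3, as 9.9 directs. The shift of 1.05 to 1.12 assumes one complete non-eater in a dose group. The documents give no rate for such events, and there may be none.
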